8.5 END OF INTERVENTION CLINIC VISIT (EOI ±3 DAYS)

The EOI Clinic Visit will occur in the last week of the intervention. The earliest it can occur is the first day of the last week, and the latest it can occur is the last day of the last week. However, data collection with the activity tracker and sleep diary should begin 7 days before the scheduled EOI. Note that the same flexibility of data collection suggested for the Baseline visit also applies to this visit. The following activities will occur at the EOI Clinic Visit:

- PROMIS 8a SRI and 8b SD
- Concomitant medication (and alternative therapies)
- Weight
- PROMIS10a Fatigue
- Neurocognitive Battery
- ECog2
- PASC Symptom Questionnaire
- Insomnia Severity Index (ISI)
- Orthostatic Hypotension Questionnaire (OHQ)
- Modified DePaul Symptom Questionnaire-Post-Exertional Malaise (DSQ-PEM)
- Patient Global Impression of Severity (PGIS)
- Patient Global Impression of Change (PGIC)
- Sleep diary, to be completed for 7 days before EOI
- Activity tracker, to be worn for 7 days before EOI at all times except when charging
- Biorepository, for blood and stool (Section 8.9)
- Safety assessment including SAEs, SUSARs, and ESIs
- Intervention adherence evaluation
- Healthcare Encounter (separate form from the safety assessment)

See each appendix for additional procedures. Refer to the MOP for details of these procedures.

8.6 EARLY TERMINATION CLINIC VISIT

Participants who discontinue the study intervention early will be asked to complete an Early Termination Clinic Visit. The Early Termination Clinic Visit should occur as soon as possible after study intervention discontinuation, preferably within ±3 days of discontinuation. Note that the same flexibility of data collection timing suggested for the Baseline visit also applies to this visit. The visit assessments match those in the End of Intervention Clinic Visit.

8.7 END OF STUDY (EOI +30 (±3) DAYS)

The End of Study timepoint is applicable for all appendices and will assess persistence or rebound of primary sleep outcomes. It will be a phone call 30 (±3 days) after the EOI or Early Termination Clinic Visit and will comprise the following activities:

- PROMIS 8a SRI and 8b SD
- Patient Global Impression of Change (PGIC)
- Safety assessment including SAEs, SUSARs, and ESIs
- Activity tracker, to be worn for 7 days before End of Study at all times (except when charging)

8.8 STUDY ASSESSMENTS

8.8.1 PRIMARY OUTCOME MEASURES

The primary outcome measure will be determined per appendix; however, all participants will complete both outcome measures, PROMIS 8a SRI and 8b SD, at each visit that requires them.

Patient-Reported Outcomes Measurement Information System (PROMIS) global health scale: The PROMIS was developed out of the "Roadmap for Medical Research" created by the NIH in 2002 as valid, generalizable items to standardize clinical research across NIH-funded research dealing with PROS. Multiple PROMIS scales have been validated across many clinical populations.³⁹ The PROMIS 8a SRI and 8b SD were developed as short forms from the PROMIS SD and SRI. The 8-item short forms strongly correlate with the long forms and have greater precision than other commonly used sleep assessments such as the Pittsburgh Sleep Quality Index and the Epworth Sleepiness Scale. They take 5 minutes to complete.

The PROMIS 8b SD form includes a total of 8 items that ask participants to reflect on their sleep over the past 7 days with one question rated very poor to very good and the remaining questions rated not at all to very much. The PROMIS 8a SRI form includes a total of 8 items that ask participants to reflect on their sleep-related daytime impairment over the past 7 days with questions rated not at all to very much.

An activity tracker will be used as an objective measure to assess sleep onset variability as a primary outcome, along with PROMIS 8b SD, only in Appendix B.

8.8.2 SECONDARY OUTCOME MEASURES

8.8.2.1 PROMIS 10A FATIGUE

The PROMIS 10a Fatigue is a 10-item questionnaire that assesses a participant's fatigue on a scale of 1 (not at all fatigued) to 5 (very much). It takes 2 minutes to complete.

8.8.2.2 NEUROCOGNITIVE BATTERY

The neurocognitive battery includes measures of objective cognitive function utilizing well-validated, psychometrically robust tests of attentional capacity, executive skill, and memory function. These measures objectively characterize the following:

Learning and Memory:

• Verbal list learning over repeated trials, free recall, and recognition memory

Executive Attentional and Processing Speed Skills:

- Timed sequencing of two sets of stimuli according to a key
- Vigilance tasks:
 - o Stimuli identification among simple distractors
 - o Stimuli identification among more complex distractors
- Verbal fluency
- Measures of attention:

o Simple reaction time; respond when X happens

o Choice reaction time; respond only if X happens

Concentration/working memory; yes/no does new stimuli match previous stimuli

8.8.2.3 EVERYDAY COGNITION 2 (ECOG2)

The ECog2 is a self-report, 41-item questionnaire used to measure the participant's perceived capacity to perform activities related to cognitive function, which could impact major activities of daily living and independence.⁴⁰ It has been used for patients with mild cognitive impairment,⁴¹ Alzheimer's Disease,⁴² and dementia.⁴³ It takes 5 minutes to complete.

8.8.2.4 PASC SYMPTOM QUESTIONNAIRE

Participants will be asked to complete a questionnaire asking about the presence of PASC symptoms at Baseline and at follow-up visits. This questionnaire includes symptoms that have been associated with PASC.

8.8.2.5 INSOMNIA SEVERITY INDEX

The ISI is a 7-item, self-report questionnaire that assesses the nature, severity, and impact of insomnia, on a 5-point Likert scale (eg, 0 = not at all, 4 = extremely; scores: from 0 to 28). The ISI asks patients to recall their insomnia symptoms over the past 2 weeks, assesses various dimensions of insomnia under the DSM-V criteria⁴⁴ and has been validated as an outcome measure for insomnia research.⁴⁵ A reduction of 6 ISI points is associated with improvements in patient-reported quality of life, productivity, and fatigue and represents a clinically meaningful within-patient improvement in individuals with insomnia.⁴⁶ It takes about 3 minutes to complete.

8.8.2.6 SLEEP DIARY

The sleep diary will request participants to log characteristics of their sleep, including bed time, sleep time, wake time, sleep quality, nap counts, nap periods, and unintended sleep. The sleep diary log presents sleep definitions to help participants complete the log.

8.8.2.7 ACTIVITY TRACKER

The activity tracker will capture participants' activity metrics, like step count, and sleep metrics, such as average nocturnal and 24-hour sleep duration, sleep efficiency, and sleep midpoint. Participants will be required to wear the activity tracker on their wrists for 7 days before and at the end of the intervention.

8.8.3 EXPLORATORY PROS

8.8.3.1 ORTHOSTATIC HYPOTENSION QUESTIONNAIRE (OHQ)

The OHQ is a measure of orthostatic intolerance, which has been the primary presentation of patients with PASC-related autonomic dysfunction. The OHQ can accurately evaluate the severity of symptoms and the functional impact of orthostatic intolerance.⁴⁷ This measure includes the Orthostatic Intolerance Daily Activity Scale and the Orthostatic Intolerance Symptom Assessment, and prior data in patients with PASC suggests that this measure discriminates well those with symptoms compared to healthy controls. It takes less than 5 minutes to complete.

8.8.3.2 MODIFIED DEPAUL SYMPTOM QUESTIONNAIRE POST EXERTIONAL MALAISE

The Modified DePaul Symptom Questionnaire Post-exertional Malaise (DSQ-PEM) is a short form of the DSQ that assesses PEM.⁴⁸ This scale assesses symptom frequency and severity over the previous 6-month period; however, for this trial, the look-back period will be modified to the previous 7 days. This short form was previously validated in patients with myalgic encephalomyelitis/chronic fatigue syndrome. It takes less than 5 minutes to complete.

8.8.3.3 PATIENT GLOBAL IMPRESSION OF SEVERITY (PGIS)

The PGIS asks participants to describe the severity of their overall status over the past week. The survey takes less than 1 minute to complete.

8.8.4 SPLIT WEEK SELF-ASSESSMENT OF SLEEP SURVEY (FOR CPSD APPENDIX)

The SASS-Y is an 18-item survey that asks participants to self-report their sleep characteristics from the previous week.⁴⁹ It takes 2 minutes to complete.

8.8.5 PATIENT GLOBAL IMPRESSION OF CHANGE

The PGIC asks participants to describe their overall status since the beginning of the study. The survey takes less than 1 minute to complete.

8.8.6 BIOMARKERS

Blood and stool samples will be collected from participants for biomarkers assessment. Biospecimens will be stored in a biorepository. Refer to the MOP for further details regarding specimen collection, preparation, and shipment.

8.9 BIOREPOSITORY FOR FUTURE RESEARCH

The RECOVER Biorepository is designed to collect and store biospecimens, such as blood plasma and serum samples, for future research related to the various studies of the RECOVER Program. Such

research might focus on developing diagnostic and/or prognostic tests, improving our understanding of the underlying pathophysiology of PASC, and developing new therapeutic targets. Samples from biorepositories have proven to be enormously important in the last 20 years, as information on the components of blood has expanded rapidly. Important insights have been gained from biorepository samples from clinical trials and the stored samples from the RECOVER Program will prove equally productive and important. This Biorepository will be conducted under the coordination of the Duke Clinical Research Institute (DCRI) which serves as the CT-DCC for all RECOVER clinical trials.

The existence of the RECOVER Biorepository will provide the opportunity to devise new hypotheses since blood collection techniques are standardized across all approved protocols, thereby allowing cross-protocol sample comparisons if scientifically justified.

Within this framework, the design of the Biorepository is to collect stool, plasma, and serum for future, as yet unspecified, analyses and studies. At each blood collection time point, 80 mL of blood will be collected to prepare the aliquots for storage at -80 °C. These samples will be stored at the Biorepository in a lab for up to 7 years. See MOP for details.

9 SAFETY ASSESSMENTS AND REPORTING

9.1 ADVERSE EVENTS AND SERIOUS ADVERSE EVENTS

9.1.1 DEFINITION OF ADVERSE EVENTS AND SERIOUS ADVERSE EVENTS

An AE is any untoward medical occurrence in humans, whether or not considered intervention-related, which occurs during the conduct of a clinical trial. An AE can therefore be any change in clinical status, routine labs, x-rays, physical examinations, etc., that is considered clinically significant by the site investigator.

An SAE or serious suspected adverse reaction or serious adverse reaction, as determined by the investigator or the sponsor, is an AE that results in any of the following serious outcomes:

- Death
- Life-threatening AE ("life-threatening" means that the study participant was, in the opinion of the investigator or sponsor, at immediate risk of death from the reaction as it occurred and required immediate intervention)
- Persistent or significant incapacity or substantial disruption of the ability to conduct normal life functions
- Inpatient hospitalization or prolongation of existing hospitalization
- Congenital abnormality or birth defect
- An important medical event that may not result in one of the above outcomes, but may jeopardize the health of the study participant or require medical or surgical intervention to prevent one of the outcomes listed in the above definition of a serious event

For those interventions that include a device, the following additional definitions will apply.

An Adverse Device Effect (ADE) is an event related to the use of an investigational medical device. This includes any AE resulting from insufficiencies or inadequacies in the instructions for use, deployment, implantation, installation, operation, or any malfunction of the investigational medical device. This also includes any event that is a result of a use error or intentional misuse.

- Device malfunction the failure of a device to perform in accordance with the instructions for use or clinical investigative plan.
- User error or intentional misuse a device is used in a manner that is an act or omission of an act that results in a different medical device response than intended by the manufacturer or expected by the user.

An Unanticipated Adverse Device Effect (UADE) is any serious adverse effect, problem, or death caused by or associated with, a device if that effect was not previously identified in nature, severity, or degree of incidence in the investigational plan or application (including a supplementary plan or application), or any other unanticipated serious problem associated with a device that relates to the rights, safety, or welfare of subjects.

Unanticipated Adverse Device Effects will include events meeting either A or B as stated below:

- A. Events meeting ALL of the following criteria:
 - Not included in the relevant appendices, product label, or instruction for use
 - Related to the investigational device per a principal investigator and/or a platform protocol principal investigator
 - Serious (meets any of the following criteria):
 - $\,\circ\,$ Is a life-threatening illness or injury
 - \circ Results in permanent impairment of a body function or a body structure
 - $\circ\,$ Necessitates medical or surgical intervention to prevent permanent
 - impairment of a body function or a body structure
 - Results in hospitalization
 - $\,\circ\,$ Led to fetal distress, fetal death, or a congenital abnormality or birth defect $\,\circ\,$ Led to death
 - (*Permanent* means irreversible impairment or damage to a body structure or function, excluding trivial impairment or damage).
- B. Any other unanticipated serious problem associated with the investigational device that relates to the rights, safety, or welfare of subjects.

Hospitalization for elective treatment of a preexisting condition that did not worsen from baseline does not meet the definition of an SAE. Hospitalization is defined as a stay in the hospital exceeding 24 hours.

An unexpected AE is defined as any AE, the specificity or severity of which is not consistent with the interventions' package insert or directions for use.

The DCRI Safety Medical Monitor will determine expectedness/listedness for SAEs and UADEs.

9.1.2 COLLECTION PERIOD OF AE AND SAE INFORMATION

Safety event collection will occur at the pre-specified study visits but all participants will be instructed to self-report concerns by calling the site.
Serious adverse events (SAEs), UADEs, or ESIs (per appendix) will be extracted by site personnel from the participant's medical record if the participant seeks medical care or if hospitalization occurs, each of which notifies the site to conduct follow-up.

Medical occurrences that begin before the first invasive study procedure (blood collection or nasal swab), but after obtaining informed consent, will not be considered an AE. The medical occurrence or condition will be captured on the Medical History electronic case report form (eCRF).

Non-serious AEs may be reported by the participant, but will not be collected into the study database as an AE or further assessed by the site or study personnel. Non-serious AEs that result in study intervention discontinuation will be identified as the reason for study intervention discontinuation in the study database and reported separately as an AE, and they will be collected from the start of study intervention administration through the end of the intervention.

Any AEs that are also classified as symptoms associated with PASC and collected during the study will not be collected as a safety event to the study database or further assessed by the site or study personnel because they will be collected as part of the PASC symptom dataset.

Serious adverse events (SAEs) will be collected from the first invasive study procedure (blood collection or nasal swab) through the End of Study for all appendices that use a study drug and through the EOI Clinic Visit for all appendices that include other interventions.

UADEs will be collected in the clinical database from the start of the intervention through the end of the intervention.

Adverse events (AEs) that qualify as an ESI, even if a non-serious AE, will be collected from the start of the study intervention through the End of Study (30 ± 3 days after EOI) for all appendices that use a study drug and through the EOI Clinic Visit for all appendices that include non-drug interventions.

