2 INTRODUCTION

2.1 STUDY RATIONALE

Post-Acute Sequelae of SARS-CoV-2 infection (PASC), also known as Long COVID, is a chronic condition that develops in up to 80% of SARS-CoV-2-infected, hospitalized patients and in 40% to 70% of non-hospitalized patients with COVID-19.¹⁻⁴ The number of individuals with PASC is rising, and the personal and global impact of PASC symptoms can be debilitating. Individuals with PASC can experience extensive symptoms, including dyspnea, autonomic dysfunction, exercise intolerance, anxiety, depression, cognitive impairment, and a wide range of sleep disturbances. Insufficient sleep, excessive daytime sleepiness, and sleep-wake disturbances can markedly impact quality of life, energy and vitality, and overall health – directly or indirectly affecting other PASC symptoms. Therefore, with the increasing number of people infected with SARS-CoV-2, an urgent and unmet clinical need exists to better understand the pathophysiology of PASC and to develop targeted interventions that restore patients' sleep health. This platform protocol aims to investigate interventions with prior evidence of improving disordered sleep and its daytime symptoms. If successful, results will enable providers to treat PASC-emergent symptoms of sleep and circadian rhythm disturbances.

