9.1.4 REPORTING AND MONITORING OF SAES FOR STUDY DRUG(S) OR UADES FOR DEVICE(S)

Study drugs used in this platform protocol are not approved for the indication for the treatment of PASC. The DSMB will review aggregate safety data according to the DSMB Charter.

Any UADE(s) that a platform protocol principal investigator determines is/are reportable will be submitted to the manufacturer, all reviewing IRBs, and all participating site investigators within 10 working days of when the platform protocol principal investigator makes that determination.

If the platform protocol principal investigator determines that a UADE presents an unreasonable risk to participants, all investigations or parts of investigations presenting that risk shall be terminated as soon

as possible. Termination shall occur no later than 5 working days after the sponsor makes this determination and no later than 15 working days after the sponsor first received notice of the effect.

Individual SAEs or UADEs must be entered into the data system within 24 hours of site awareness. After receiving that data, within 1 to 2 business days the DCRI Safety Surveillance team will notify pharmaceutical partners of SAEs (if applicable) and device manufacturers of UADEs that occur involving the specific appendix of the supplied study drug/control or supplied device, as required.

Serious adverse events (SAEs) that are related to the study drug and confirmed unlisted by the DCRI Safety Medical Monitor and platform protocol principal investigator will be reported to the central IRB as SUSARs — as 7-day reports for unexpected fatal or life-threatening adverse reactions and 15-day reports for serious and unexpected adverse reactions. The SUSARs will be shared with the pharmaceutical partner of the supplied study drug according to the same timelines, if applicable. If the DSMB notes a clinically important increase in the rate of a SUSAR, the platform protocol principal investigator will notify site investigators no later than 15 calendar days after determining that the information qualifies for reporting. The site investigators will notify their local IRBs according to local guidelines, if applicable. Refer to the Safety Management Plan for details regarding specific reporting timelines.

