13.6 EVENTS OF SPECIAL INTEREST

The following ESIs will be collected for Appendix A:

- Hypertension
 - Rhinitis Pharyngitis
- Headache
- Rash
- DiarrheaNausea/vom
- Nausea/vomiting
 Backpain
- Psychiatric event
- Back pain

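### Section 9.1.2 both excludes and requires collection of adverse events that are also PASC symptoms, and does not say which rule prevails

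*Protocol*

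**What the plan says.** The rules on collection (Protocol 9.1.2, 9.1.3 and 9.1.4):

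- **PASC-symptom exclusion (9.1.2):** "Any AEs that are also classified as symptoms associated with PASC and collected during the study will not be collected as a safety event". The sentence goes on to bar these events from being entered in the study database "or further assessed by the site or study personnel because they will be collected as part of the PASC symptom dataset".
- **ESIs (9.1.2):** "Adverse events (AEs) that qualify as an ESI, even if a non-serious AE, will be collected from the start of the study intervention". In appendices with a study drug, collection runs to End of Study, 30 ± 3 days after EOI.
- **SAEs (9.1.2):** "Serious adverse events (SAEs) will be collected from the first invasive study procedure (blood collection or nasal swab) through the End of Study" in drug appendices, and through the EOI visit in the others. Section 9.1.4 adds: "Individual SAEs or UADEs must be entered into the data system within 24 hours of site awareness".
- **Other non-serious AEs (9.1.2, the paragraph before the exclusion):** not collected, except that those causing discontinuation of the intervention are recorded and reported as AEs.
- **Worsening (9.1.3):** a condition present at screening that deteriorates is to be recorded as a safety event.

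The terms that may overlap:

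- Section 13.6 lists nine ESIs for Appendix A, among them "Psychiatric event".
- Section 2.1 describes PASC symptoms as including "dyspnea, autonomic dysfunction, exercise intolerance, anxiety, depression, cognitive impairment, and a wide range of sleep disturbances".

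The dataset offered as the substitute (8.8.2.4): "Participants will be asked to complete a questionnaire asking about the presence of PASC symptoms at Baseline and at follow-up visits". Table 2 schedules this questionnaire at Baseline and EOI only, and the End of Study call in section 8.7 does not include it.

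**The concern.** The exclusion is worded to cover every AE that is also a PASC symptom. For such an event a site has two instructions: leave it out and do not assess it, or collect it because it is an ESI, an SAE or a reason for discontinuation. Either course follows the protocol.

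This matters because the safety dataset is deliberately small. The safety analysis in section 10.4.3 rests on SAEs, ESIs and AEs or SAEs leading to discontinuation. Ordinary non-serious AEs are not collected, so nothing else would show what was left out. In Appendix A the overlap falls where the protocol itself expects drug effects. Section 13.4.1 lists anxiety and nervousness among the common AEs of modafinil. Section 13.5.1 names serious psychiatric events as a risk of solriamfetol and reports anxiety as more frequent than on placebo.

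**Working it through.** There is no planned figure to reproduce. The check sets the provisions against each other.

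**1. Does the exclusion have a limit?** It contains none for seriousness, ESI status or discontinuation. Section 9.1.1 defines an SAE as a kind of AE, so on its literal terms the sentence reaches SAEs too. The ESI and SAE sentences have no exception for PASC symptoms.

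**2. Can it be read down to ordinary non-serious AEs?** The preceding paragraph already keeps those out of the database. Under that reading the exclusion would remove almost nothing that is otherwise collected. It has real effect only if it removes ESIs, discontinuation AEs or SAEs. Reading it narrowly is therefore possible but makes it nearly redundant, and the text does not direct it.

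**3. Is there an event that both rules cover?** A new or worse anxiety or depressive episode is plausibly both a PASC symptom (section 2.1) and a psychiatric event (section 13.6). That is one of nine ESI terms. Headache, diarrhea and nausea might also overlap, but the questionnaire's items are not in the protocol, so this is not shown. Appendix B has no ESIs (section 14.7), so the ESI conflict is confined to Appendix A. The SAE, discontinuation and worsening conflicts apply to both appendices.

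**4. Could the questionnaire replace safety reporting?**

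- *Content.* It is described as recording whether symptoms are present. Sections 9.1.2.2 and 9.1.3 require relationship, onset and severity for reportable events, while the exclusion rules out further site assessment.
- *Timing in Appendix A.* ESI collection covers about 10 weeks of drug plus 30 days: 70 + 30 = 100 days. The Baseline questionnaire belongs to the visit before the intervention starts, so one administration, at EOI, falls in that window. None falls in the last 30 days. An overlapping ESI that begins after EOI would be in neither dataset at a site that applies the exclusion.
- *Use.* Section 10.4.3 analyzes the questionnaire's total score as a secondary efficacy endpoint, so a drug effect could appear only as a change in that score.

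**5. What happens to the counts?** Suppose a fraction r of overlapping ESIs is reported because sites read the rule differently. The observed count is r times the true count. Randomization is stratified by site (section 6.3) and Appendix A is double-blind, so r should be similar in the two arms. The ratio between arms is then roughly preserved, the absolute difference shrinks to r times its true value, and precision falls. The protocol gives no basis for r.

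**6. Halting rule, literal reading only.** Section 13.3 acts on three or more related SAEs of one type on the same drug. Suppose each such SAE were left out with probability q, an assumed value.

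| q | Exactly 3 SAEs: probability all are counted, (1 − q)³ | 5 SAEs: P(X ≥ 3), X ~ Binomial(5, 1 − q) |
|---|---|---|
| 0 | 1.00 | 1.00 |
| 0.10 | 0.73 | 0.99 |
| 0.25 | 0.42 | 0.90 |
| 0.50 | 0.125 | 0.50 |

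Nothing in the protocol suggests a value of q above zero, and the conclusion does not rest on this table.

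**The case against.** The best reply is that the section can be read sensibly as it stands. The exclusion follows the paragraph on non-serious AEs and echoes its wording, so it may belong to that paragraph. The ESI sentence comes later, is more specific and expressly reaches non-serious events. It already overrides the general rule against collecting them and would override the exclusion in the same way. This makes the benign reading likely, but it remains an inference. The protocol states no precedence, and the reading leaves the exclusion with almost no function.

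On SAEs the reply is stronger. Section 9.1.2 requires their collection and their extraction from the medical record when care is sought. Section 9.1.4 sets 24-hour entry without qualification. Safety assessments in sections 8.4.2, 8.5 and 8.7 cover SAEs. The reason given for the exclusion, that the symptom dataset captures the event, does not fit a hospitalization.

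On overlap, section 2.1 is background and the exclusion is tied to symptoms collected in the study. The count of more than 200 PASC symptoms in section 2.2 therefore cannot be used to size it. That stands, and it limits the overlap to a plausible one for psychiatric events.

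Finally, sites speak to participants often: titration calls about every 5 days for about 20 days, and a safety call at 42 ± 7 days. Sites would therefore often hear of events. The gap is in whether they record and assess what they hear.

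**Conclusion.** The contradiction is real and can be verified within section 9.1.2, with section 9.1.3 adding to it. Its demonstrable reach is one of the nine Appendix A ESI terms, on the assumption that anxiety or depression would be classed both as a PASC symptom and as a psychiatric event. For such an event, literal application loses onset, severity and relatedness, and loses the event altogether if it starts after EOI. If sites differ, ESI incidence is understated by an unknown amount.

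A reader might infer that the protocol suppresses ESIs, blinds the DSMB or disables the halting rule. The documents do not support that. They also require ESI and SAE collection, and loss of SAEs would need a site to set aside several explicit duties. Nor is a bias between arms shown, since one site's reading would apply to both of its arms. The defect is an unresolved conflict between instructions, in the part of the plan that produces nearly all of the safety data.

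**What to change.** Reconcile the passages with one sentence in section 9.1.2. It should state that the PASC-symptom exclusion is limited to non-serious AEs that are not ESIs. It should add that the exclusion does not apply to SAEs, SUSARs, UADEs, ESIs or AEs leading to discontinuation, and that these are recorded as safety events even when they are also PASC symptoms, including when they are a worsening from baseline. Section 9.1.3 should cross-refer to that sentence so that the rule on deterioration agrees with it.

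The cost is a protocol clarification, a memo to sites and slightly more event entry. No visit, assessment, dose or analysis changes.
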